14.3.2 Other efficacy analyses

The secondary variables and change from Baseline in QMG score, MG-Composite score, MGADL score, MGII score, muscle weakness severity and fatigability scale score and fatigue scale score, at each assessed post-Randomization Visit (during Dosing Period 1 including Visit 9) will also be analyzed utilizing the MMRM approach similarly to the change from Baseline in QMG for the FAS as described in Section 14.3.1.

QMG, MG-Composite, and MGADL responder rates at each assessed post-Randomization Visit (during Dosing Period 1) will be compared between the 2 Treatment Groups utilizing Fisher's exact test.

The percentage of subjects with each MGFA classification at each scheduled assessment during Treatment and Observation Periods will be calculated.

Psychometric analyses of the newly developed measures MG muscle weakness severity and fatigability and fatigue scales will be performed blinded from treatment arms. The association between PROs and clinical variables will also be explored, as well as the association between the various PROs. A psychometric analysis of the MG muscle weakness severity and fatigability scale and fatigue scale using Rasch analysis will be performed, but reported separately from the CSR.

Changes in MCD of the IPI, and normal fiber pairs in jitter (SFEMG) will be summarized using descriptive statistics, by treatment group and time point, including changes from Baseline. A reduction in MCD of $\geq 9\mu s$ in jitter (SFEMG) studies will also be summarized using descriptive statistics, by treatment group and time point, including changes from Baseline.

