- Dosing Period 1 will be 4 weeks, with 2 parallel Treatment Groups (UCB7665 7mg/kg or placebo).
- Dosing Period 2 will be 2 weeks, with 2 parallel Treatment Groups (UCB7665 7mg/kg or UCB7665 4mg/kg).

variations thereof Prior to receiving an infusion with IMP, subjects will be assessed for efficacy measurements at each visit in the Treatment Period. For all safety and efficacy measurements, the order specified in the Study Procedures Manual is recommended to be used as a guide.

Dosing Period 1: Dosing Period 1 will last for approximately 4 weeks (Day 1 to Day 28) and includes Visits 2, 3, 4, 5, 6, 7, and 8. Following completion of the Screening Period, eligible subjects will check-in at the clinic/hospital for the Randomization Visit (Visit 2). Subjects who continue to meet eligibility requirements will be randomized 1:1 to receive 7mg/kg of UCB7665 or placebo, administered by an approximately 30 minute sc infusion at weekly intervals for 3 weeks (Visits 2, 4, and 6) followed by an assessment visit at Week 4 (Visit 8). At Visits 2, 4, and 6 in Dosing Period 1, subjects will be required to remain in the clinic/hospital for at least 4 hours for safety monitoring after the infusion. Subjects may leave the clinie/hospital once the safety monitoring postdose period is over and the investigator or designee has no safety concerns. A follow-up telephone call will be conducted 24 hours postdose to assess the status of the subject (Visits 3, 5, and 7). Subjects will return to the clinic/hospital at Visit 8 for safety and efficacy assessments (see Section 5.2, Schedule of Study Assessments). The primary efficacy endpoint, change from Baseline in the QMG score, will be assessed at the beginning of Dosing Period 2 at Visit 9 (Day 29) prior to rerandomization. The efficacy assessments that are performed at Visit 9 will therefore occur 2 weeks after the final dose of study drug in Dosing Period 1.

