5.1.3 Planned number of subjects and sites

To ensure that at least 40 subjects are evaluable for the primary efficacy variables, a sample size of approximately 42 randomized subjects is planned at approximately 30 sites to achieve the targeted number of 40 evaluable subjects.

Anticipated regions and countries

It is planned to recruit subjects in USA, Canada, and Europe in this study, with possible extension to other regions and countries.

5.1.4

REPACTOR CONTRACTOR OF THE CON

Table 5.1: Schedule of assessments

Clinical Study F	rotocol								UCE	37665	5											MG000
Table 5.1:	Sche	edule of	ass	essm	ents	5															ionsti	
Assessments	Screen	ing	Trea	tment I	Period											Obs	serva	tion F	Period	L adic	7	UV
		r	Dosi	ng Peri	od 1		1			Dos	ing Pei	iod 2	n	I	r		I		05	•		
	Visit	1	2 BL	3 ^b	4	5 ^b	6	7 ^b	8	9	10 ^b	11	12 ^b	13	14 ^b	15	16	J.	18	19	20 FV/PEOT c	
	Day	-28 to -1	1													500	57	64	78	92	99	
				$ \begin{array}{c ccc} (\pm 2 \\ days) \end{array} \begin{pmatrix} (\pm 2 \\ days) \end{pmatrix} $													(± 2	days)			$(\pm 2 \text{ days})$	
Written informed	consent	Х											×.	lor	 							
Written informed for genomic subst		Х								Ċ	182		2P/100									
Demographic data		Х							\sim	\sim		5										
Verification of ind exclusion criteria		Х	Х						ACT Y		122											
Call or enter IRT register the visit	to	Х			Х		Х	X		Jill		Х		Х							Х	
Call or enter IRT/ Randomization	r		X						x etims	Х												
Withdrawal criter	ia		Х	Х	Х	Х	Х	XC	X	Х	Х	Х	Х	Х	Х	Х	Х	Х	Х	Х		
General medical/ procedures history	y	Х					X	\mathcal{T}														
Prior and concom medication	itant	Х	Х	Х	x	XQ	X	Х	Х	Х	Х	Х	Х	Х	Х	Х	Х	Х	Х	X	Х	X
Concomitant med procedures	ical		Х	e	×® >		Х		Х	Х		Х		Х		Х	Х	Х	Х	Х	Х	X
Vital signs ^f		Х	Х	2 150	Х		Х		Х	Х		Х		Х		Х	Х	Х	Х	Х	Х	X
Body weight, heig		Х	, v v							Х											Х	
Recording of AEs		x	X	Х	Х	Х	Х	Х	Х	Х	Х	Х	Х	Х	Х	Х	Х	Х	Х	Х	Х	X
Confidential	15 docu	nent	X X 							Table 5.1: Schedule of assessments

UCB Clinical Study P	rotocol								UCE	37665	5										L'ere	Sep 2017 MG0002
Table 5.1:	Sche	edule of	ass	essm	ents	5														4	iions th	
Assessments	Screen	ing	Trea	atment I	Period											Obs	serva	tion P	eriod	$-\cdot$		UV
			Dosi	ing Peri	od 1	l	1		1	Dos	ing Pe	iod 2		I	r		I	6	5			
	Visit	1	2 BL	3 ^b	4	5 ^b	6	7 ^b	8	9	10 ^b	11	12 ^b	13	14 ^b	15	16	9	18	19	20 FV/PEOT c	

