Unless stated otherwise, all statistical tests will be 1-sided and conducted at 0.05 alpha levels (due to the character of the study no alpha adjustment for multiplicity will be done). For Dosing Period 2, only descriptive analyses will be performed.

Data listings containing all documented data and all calculated data will be generated.

Baseline will be the last non-missing data collected prior to the first dose of IMP in Dosing Period 1, and measurement-specific Baseline values will be defined in the SAP.

Planned efficacy analyses 14.3

For all efficacy analyses the Treatment Groups used for analysis during Dosing Period 1 and during Dosing Period 2/Observation Period will be as defined in Section 14.2. Efficacy endpoints will be analyzed using descriptive statistics for data obtained during Treatment Period 2 and Observation Period. Further details will be provided in SAP.

ر 14.3.1 Analysis of the primary efficacy variable

The primary efficacy variable is the change from Baseline in QMG score to Visit 9 (Day 29), prior to the first infusion of IMP in Dosing Period 2.

A 1-sided hypothesis test will be performed to test the primary hypothesis of superiority of UCB7665 7mg/kg vs placebo at Visit 9. The null hypothesis is that there is no difference in the change from Baseline between Treatment Groups. The alternative hypothesis is that the mean change from Baseline in QMG score is smaller in the UCB7665 7mg/kg group than the placebo group.

The primary analysis of the primary variable will be based on a mixed model repeated measures (MMRM) analysis of covariance (ANCOVA) that includes terms for treatment group, week, the Baseline QMG score, and the interaction between treatment group and week. The model will define patient as a random effect and utilize an unstructured covariance pattern.

Least Squares (LS) Means for changes from Baseline at Visit 9 for each treatment group will be presented together with LS mean differences (UCB7665 - 7mg/kg vs placebo) and 1-sided 95% confidence interval (CI).

For subjects who prematurely withdraw for any reason before Visit 9 (Day 29), data collected during the PEOT Visit will be used to impute QMG scores at the next consecutive visit.

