2.2.1.3 Other efficacy variables

The other efficacy variables are:

- Value and change from Baseline in QMG at each scheduled assessment during Treatment and Observation Periods
- QMG responder (≥ 3.0 point improvement from Baseline) at each scheduled assessment during Treatment and Observation Periods
- Value and change from Baseline in MG-Composite score at each scheduled assessment during Treatment and Observation Periods
- MG-Composite responder (≥ 3.0 point improvement from Baseline) at each scheduled assessment during Treatment and Observation Periods
- Value and change from Baseline in MGADL at each scheduled assessment during Treatment and Observation Periods
- MGADL responder (≥ 3.0 point improvement from Baseline) at each scheduled assessment during Treatment and Observation Periods
- Myasthenia Gravis Foundation of America (MGFA) classification at each scheduled assessment during Treatment and Observation Periods
- Value and change from Baseline in MG muscle weakness and fatigability at each scheduled assessment during Treatment and Observation Periods
- Value and change from Baseline in fatigue at each scheduled assessment during Treatment and Observation Periods
- Value and change from Baseline in Myasthenia Gravis Impairment Index (MGII) scores at each scheduled assessment during Treatment and Observation Periods
- Value and change from Baseline in MGII ocular sub-scores at each scheduled assessment during Treatment and Observation Periods
- Value and change from Baseline in MGII generalized domain sub-scores at each scheduled assessment during Treatment and Observation Periods
- Change in the percentage of normal fiber pairs in jitter [single fiber electromyography (SFEMG)] studies from Baseline to Visit 9 for the subjects consenting to this measurement at the participating sites
- Change in mean consecutive difference (MCD) of the interpotential interval (IPI) in jitter (SFEMG) studies from Baseline to Visit 9 for the subjects consenting to this measurement at the participating sites
- A reduction in MCD of $\geq 9\mu\text{s}$ in jitter (SFEMG) studies will define clinically meaningful improvement

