8.3.6 Responder rates

QMG, MG-Composite, and MGADL responder rates will be summarized at each assessed post-Randomization Visit (during Dosing Period 1) and compared between the 2 Treatment Groups utilizing Fisher's exact test for each visit for the FAS.

The frequency of attained point improvement will be plotted against treatment for Visit 9 (Week 8). For each point improvement the test result will be displayed in a table and in the plot.

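### Responder rates: Fisher's exact test is valid but, at about 20 per arm, uses only about half of the stated one-sided 5% level; Boschloo's exact test would recover power cheaply (low priority)

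*Protocol*

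**What the plan says.** Protocol 14.3.2 specifies that responder rates on the three scales "during Dosing Period 1) will be compared between the 2 Treatment Groups utilizing" Fisher's exact test. SAP 8.3.6 gives the same instruction: "compared between the 2 Treatment Groups utilizing Fisher's exact test for each visit for the FAS". Neither section states a sidedness or level, so the general rule in Protocol 14.2 and SAP 3.1 governs: "Unless stated otherwise, all statistical tests will be 1-sided and conducted at 0.05 alpha levels".

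A responder is defined by a cut of at least 3.0 points on each scale ("point improvement from Baseline) at each scheduled assessment during Treatment and Observation Periods"). The definition sits under other efficacy variables in Protocol 4.1.3 and SAP 2.2.1.3, so it is neither primary nor secondary.

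On size, Protocol 5.1 says subjects "will be randomized 1:1 to receive 7mg/kg of UCB7665 or placebo" in Dosing Period 1, and Protocol 5.1.3 says "a sample size of approximately 42 randomized subjects is planned at approximately 30 sites to achieve the targeted number of 40 evaluable subjects". That gives about 20 evaluable subjects per arm. SAP 8.3.6 also plots attained point improvement by treatment for Visit 9 and shows a test result for each point threshold.

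No responder rate, power figure or sample size is given for this comparison. SAP 8.3.6 summarises the rates but plans no rate difference and no confidence interval. The continuous endpoints, by contrast, get a least-squares mean difference with a one-sided 95% interval.

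**The concern.** Fisher's test conditions on the total number of responders. With 20 per arm the conditional distribution has few attainable p-values, so the largest one at or below 0.05 is often well below it. The test then runs at a true level far under the 5% that the plan declares. The sponsor chose a one-sided 5% level without multiplicity adjustment, and this comparison does not use it.

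An exact test with the same guarantee and more power exists. What is at stake is efficiency: a responder difference that an equally rigorous exact test would call significant at the plan's own level can be reported as not significant.

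Counting from Table 5.1, QMG and MG-Composite are assessed at Visits 4, 6 and 8, and all three scales at Visit 9. That makes six scheduled tests, or nine if Visit 9 is included, besides the threshold tests in SAP 8.3.6.

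**Working it through.** **Inputs.** Level 0.05, one-sided (Protocol 14.2, SAP 3.1). Arms n1 = n2 = 20, from 40 evaluable subjects at 1:1 (Protocol 5.1 and 5.1.3). Response rates are assumptions. The plan states no power for responders, so there is no figure of its own to reproduce. Its statement of more than 90% power concerns mean QMG change, with redacted inputs.

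**Formulas.** Let x be responders on active and y on placebo.

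- Fisher: p_F(x, y) = Σ_{k ≥ x} C(n1, k)·C(n2, x+y−k) / C(n1+n2, x+y). Reject if p_F ≤ 0.05.
- Boschloo: p_B(x, y) = max over π of P_π(p_F ≤ observed p_F), with both arms binomial at common rate π. Reject if p_B ≤ 0.05.
- Size = max over π of the rejection probability (π from 0.001 to 0.999). Power = the sum of binomial products over the rejected tables.

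The set of tables with p_F ≤ 0.05 has size at most 0.05, so Boschloo rejects every table that Fisher rejects.

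**Size, by enumerating all tables (21 × 21 = 441 at 20 per arm).**

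| Arms | Fisher, maximum | Boschloo, maximum |
|---|---|---|
| 18 vs 18 | 3.3% | 4.7% |
| 19 vs 19 | 2.9% | 4.9% |
| 20 vs 20 | 2.7% (2.66%) | 4.3% (4.28%) |
| 20 vs 21 | 3.0% | 4.8% |
| 21 vs 21 | 2.4% | 4.4% |

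At 20 vs 20, Fisher's true level is 0.8% at a common rate of 10%, 2.3% at 20%, 2.7% at 30% and 2.1% at 50%.

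**What changes.** At 20 vs 20 Boschloo's region is p_F ≤ 0.0776. It adds 11 of the 441 tables, with Fisher p from 0.053 to 0.078. For example, with 11/20 active and 5/20 placebo, p_F = Σ_{k=11}^{16} C(20, k)·C(20, 16−k) / C(40, 16) = 0.053, while p_B = 0.030. The observed difference is 55% − 25% = 30 points.

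**Power at 20 vs 20 (assumed rates).**

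| Placebo vs active | Fisher | Boschloo | Gain, points |
|---|---|---|---|
| 35% vs 65% | 45.3% | 57.3% | 12.0 |
| 30% vs 60% | 46.3% | 57.5% | 11.2 |
| 25% vs 60% | 61.0% | 70.7% | 9.7 |
| 20% vs 50% | 53.1% | 61.2% | 8.1 |
| 15% vs 60% | 87.3% | 91.2% | 4.0 |
| 15% vs 70% | 96.3% | 98.0% | 1.7 |

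The range was taken over placebo rates of 10% to 50% in 5-point steps, wherever Fisher's power lies between 30% and 90%. The gain is 4.0 to 12.0 points at 20 per arm and 5.4 to 12.6 at 21 per arm, hence roughly 4 to 13. Other arm sizes can give less: for 30% vs 60%, 49.3% to 52.7% at 18 per arm (3.4 points), and 53.3% to 57.6% with 20 active and 21 placebo (4.3 points).

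**The case against.** The case for leaving the plan alone is reasonable, and much of it stands.

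- **Fisher's test is not an error.** It is pre-specified and holds the false-positive rate below 5%. A reader might infer a flaw that biases results or inflates error; nothing in the documents supports that. This is lost efficiency.
- **The endpoint is low in the hierarchy.** No power is promised for it, and the same three scales are analysed as continuous changes by MMRM or ANCOVA. An effect is not missed merely because a responder p-value is 0.053.
- **No go/no-go role is documented.** A reader might infer that these tests drive the decision after a Phase 2a trial. Protocol 14.7 and SAP 4.4 base futility on QMG, MG-Composite and MGADL data under rules in a DMC charter that is not among the documents. The third interim analysis is described as delivering only the mean-change primary and secondary variables.
- **The 2.7% ceiling is not firm.** It belongs to exactly 20 vs 20, and per-visit numbers in the FAS will vary.
- **Multiplicity is unadjusted, so more power means more false positives.** If nine tests were independent, which they are not, the chance of at least one false positive at the maximum sizes would be 1 − (1 − 0.0266)^9 = 22% with Fisher and 1 − (1 − 0.0428)^9 = 33% with Boschloo. Both lie below the 1 − 0.95^9 = 37% implied by the plan's own per-test level. The increase is a real cost, but one that the plan already accepts.
- **The count of nine is an interpretation.** The responder sentence in Protocol 14.3.2 names Dosing Period 1 without adding Visit 9, as the preceding sentence does. SAP 8.3.6 does mention Visit 9.

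None of this disputes that Boschloo's test dominates Fisher's at the same guaranteed level.

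**Conclusion.** The point holds as a cheap, low-priority improvement. With arms of 18 to 21, Fisher's test has a true one-sided error of at most about 2.4% to 3.3% against the stated 5%, and at most 2.7% at 20 vs 20. Compared with Boschloo's test it gives up roughly 4 to 13 points of power at 20 or 21 per arm where power is moderate. The loss falls to about 2 points where power is near 96%, and can be smaller at other arm sizes.

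The size figures depend only on arm sizes and the one-sided 0.05 rule. The power figures also depend on assumed response rates. The primary and secondary conclusions are untouched, and the documents do not support calling the plan invalid or tying it to a development decision.

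**What to change.** In Protocol 14.3.2 and SAP 8.3.6, replace Fisher's exact test with Boschloo's exact unconditional test, one-sided at 0.05, computed at the arm sizes observed at each visit. Name this one test only. Leaving Barnard's test open as an alternative would leave the result undetermined for some tables: at 20 vs 20, 8/20 against 3/20 is significant by Boschloo and not by Barnard.

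In the same place, add the difference in response rates (7 mg/kg minus placebo) with an exact unconditional confidence interval at each visit, and state the interval's level and construction. This addition is useful whichever test is kept.

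The cost is about a sentence in each document and a different software option, with no extra subjects or data. The downside to record is that the maximum per-test false-positive rate at 20 per arm rises from about 2.7% to about 4.3%, within the stated 5%, across several unadjusted tests.

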14.4 Planned other and exploratory analyses

14.4.1 Safety analyses

For all safety analyses the Treatment Groups used for analysis during Dosing Period 1 and during Dosing Period 2/Observation Period will be as defined in Section 14.2 and as described in the SAP.

ationsthereof The absolute and relative frequencies for subjects with a given TEAE with respect to the preferred term according to the latest available version of the Medical Dictionary for Regulatory Activities, as well as the absolute frequencies of the individual TEAEs that have occurred, will be determined within each system organ class. Additional tables will summarize TEAEs by maximum intensity and causal relationship with IMP, as judged by the investigator. Adverse events will be categorized by severity according to the CTCAE Version 4.03 grading. In case the CTCAE grading is not available, the intensity (mild/moderate/severe) will be utilized. For the purpose of the tabulations CTCAE grades will be aligned with the intensity classifications (mild/moderate/severe) to enable pooling of the AEs in the summaries. The TEAEs leading to discontinuation of IMP and treatment-emergent SAEs will also be summarized. The action taken, time of onset relative to dosing, and duration of each AE will be listed only.

Adverse events will be assigned to a Dosing Period based on the start date of the event relative to the first dose of IMP received in the respective period.

For the continuous laboratory variables, the values and changes from Baseline will be summarized at each time point. For categorized values according to the reference range, shift tables from Baseline to each post-Baseline time point will be presented for selected variables to be defined in the SAP. Values outside the reference range will be flagged in the data listings.

Exploratory safety biomarkers will be summarized by treatment group and visit using descriptive statistics.

Normal vs abnormal findings with regard to the various ECG parameters and the overall ECG will be analyzed as required. The focus of the 12-lead ECG analysis will be the identification of outliers and of any trends for changes following administration of UCB7665 with respect to QT/QTc. Descriptive statistics will be presented for ECG value and changes from Baseline over time based on the mean of the triplicate assessments at each time point.

Descriptive statistics will be reported for all vital sign measurements (including pulse rate, systolic/diastolic BP, temperature, and respiratory rate). Measured values and changes from Baseline will be summarized by treatment group.

Physical and neurological examination findings and the results of any pregnancy testing will be presented in listings only.

Pharmacokinetic analysis 14.4.2

The PK variable is the plasma concentration of UCB7665. Pharmacokinetic parameters such as C_{max} and area under the curve will not be derived (eg, by non-compartmental analysis) due to the Stimited sampling performed at each visit.

Individual concentrations of UCB7665 will be listed and summarized at each scheduled time point. Descriptive statistics of concentrations will be calculated only if at least two thirds of the individual data points are quantifiable (≥lower limit of quantification [LLOQ]). Summaries will include the number of available observations, mean, median, SD, minimum, maximum, geometric mean, and geometric coefficient of variation (assuming log-normally distributed data). Values below the LLOQ will be reported with a clear sign indicating that they were below the LLOQ. Individual concentrations of UCB7665 will also be displayed graphically.

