AE=adverse event; BAFF=B-cell activating factor; BL=Baseline; BP=blood pressure; CSF=cerebrospinal fluid; CT=computed tomography; DNA=deoxyribonucleic acid; ECG=electrocardiogram; FV=Final Visit; GI=gastrointestinal; HIV=human immunodeficiency virus; IgA=immunoglobulin A; IgE=immunoglobulin E; IgG=immunoglobulin G; IGRA= interferon-gamma release assay; IgM=immunoglobulin M; IMP=investigational medicinal product; IRT=interactive response technology; LP=lumbar puncture; MG=myasthenia gravis; MGADL=myasthenia gravis-Activities of Daily Living; MGFA=Myasthenia Gravis Foundation of America; MRI=magnetic resonance imaging; PEOT=premature end of treatment; PK=pharmacokinetics; PR=pulse rate; RNA=ribonucleic acid; QMG=Quantitative Myasthenia Gravis; B; SFEMG=single fiber electromyogram; TB=tuberculosis; UV=Unscheduled Visit

^a Subjects will return to the clinic/hospital for Visits 15, 16, 18, and 20; for Visits 17 and 19 subjects will either return to the clinic/hospital, or, if possible and agreed by both the investigator and subject, have home visits conducted by certified healthcare professionals.

^b This visit is a telephone contact 24 hours post-IMP dose start.

^c Subjects who withdraw early will be encouraged to complete the PEOT Visit plus the FV (approximately 8 weeks after the final study drug administration).

^d A visit window of ± 2 days is allowed for the dosing visits. The visit window of ± 2 days is relative to the first dosing visit date. However, there should be a minimum interval of 5 days and maximum interval of 9 days as compared to the previous dose.

^e Includes consent for jitter (SFEMG) for the subjects consenting to this measurement at the participating sites. Additional informed consent is needed for participation in the exploratory genomic substudy.

^f Systolic and diastolic BP, pulse rate, temperature, and respiratory rate. On dosing days, vital signs will be measured prior to IMP administration, 15 minutes after the start of the infusion, at the end of the infusion, 2 hours after the end of infusion and 4 hours after the end of the infusion. At nondosing visits, vital signs need only be taken once during the visit.

Confidential

Page 29 of 193

- ^g Body weight at Screening and at Visit 9 will be used for calculation of dose; height will be assessed only at Screening.
- ^h In addition to Screening and the FV, a full neurological examination should be performed for any subject who experiences severe headache.

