12.3.3 Vital signs

Vital signs will be measured at all visits as indicated in the schedule of study assessments (Table 5.1).

Vital signs to be assessed are as follows:

- Pulse rate
- Systolic/diastolic BP
- Temperature (oral preferred, ear or axillary allowed)
- Respiratory rate

or variations thereof Subjects will be sitting for at least 5 minutes prior and during the measurement of BP, PR, and respiration rate. On dosing days, vital signs will be measured prior to IMP administration, once during the infusion (at the halfway time point), at the end of infusion, 2 hours after end of infusion, and 4 hours after end of infusion. At nondosing visits, vital signs need only be taken once during the visit.

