3.3 Definition of Baseline values

Baseline will be the last available predose value prior to the first infusion of study drug in Dosing Period 1, or if missing, the Screening values. Scheduled or unscheduled measurements can be used as the Baseline value. Expected measurement-specific Baseline time points are presented in Table 3–1. If an unscheduled measurement occurs after the planned baseline measurement time point but before dosing, then the unscheduled measurement will be used.

Table 3–1: Expected Baseline Visits

Measurement	Baseline
Safety data 
 • Clinical Chemistry • Hematology • Urinalysis • ECG • Vital signs • [REDACTED] • [REDACTED] • [REDACTED] • Body weight 	
 • Clinical chemistry, Hematology, Urinalysis, ECG and Vital signs: Predose Day 1 or if missing the Screening value • [REDACTED] [REDACTED] [REDACTED]: Predose Day 1 • Body weight: screening visit

Table 3–1: Expected Baseline Visits

Measurement	Baseline
Pharmacodynamic data 
 Total serum IgG Serum IgG subclass concentrations MG specific antibodies (██████████) 	
 Total serum IgG and Serum IgG subclass: Predose Day 1 or if missing the Screening value Mg-specific autoantibodies: Predose Day 1
Immunological data: 
 IgM, IgE, IgA Serum complement levels (C3 and C4) and plasma complement levels (C3a and C5a) ██████████ Serum BAFF levels Cytokines ██████████ specific IgG antibodies Exploratory biomarkers relating to mechanism of action, disease activity, treatment response, and clinical outcome 	
 IgM, IgE, IgA, C3, C4, C3a, C5a, ██████████, BAFF, cytokines: Predose Day 1 ██████████ antibodies: Screening Exploratory biomarkers: Predose Day 1
Efficacy data: 
 QMG scale MG-composite scale MGADL MGFA scale MG muscle weakness Fatigue MGII SFEMG 	
 QMG, MG composite scale and MGFA: Predose Day 1 or if missing the Screening value MGADL, Muscle weakness, Fatigue scale, MGII, SFEMG: Predose Day 1.

██████████ BAFF=B-cell activating factor ; Ig=immunoglobulin; MGADL=myasthenia gravis-Activities of Daily Living; MGFA=Myasthenia Gravis Foundation of America; MGII= Myasthenia Gravis Impairment Index; SFEMG=single fiber electromyography; QMG=quantitative myasthenia gravis

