Haematology	Haemoglobin increased	Hemoglobin	increase >4 over ULN or increase >4 above Baseline (if Baseline is above ULN)	mg/dL
Haematology	Lymphocyte count decreased	Lymphocytes	<500 (<0.5)	/mm ³ (10 ⁹ /L)
Haematology	Lymphocyte count increased	Lymphocytes	>20,000 (>20)	/mm ³ (10 ⁹ /L)
Haematology	Neutrophil count decreased	Neutrophils	<1000 (<1)	/mm ³ (10 ⁹ /L)

Table 14-7: TEMA/PCS Values for Rozanolixizumab Clinical Development Program Based on CTCAE Grades

Domain	Term	Test	Criteria	Unit
Haematology	Platelet count decreased	Platelets	<50,000 (<50)	/mm ³ (10 ⁹ /L)
Haematology	Leukocytosis	WBC	>20,000	/mm ³
Haematology	White blood cell decreased	WBC	<2000 (<2)	/mm ³ (10 ⁹ /L)
Haematology	Monocytes increased	Monocytes	>2000 (>2)	/mm ³ (10 ⁹ /L)
Vital Signs	Hypertension	Blood pressure systolic	≥180 and an increase from Baseline of ≥15	mmHg
Vital Signs	Hypertension	Blood pressure diastolic	>105 and an increase from Baseline of ≥15	mmHg
Vital Signs	Hypotension	Blood pressure systolic	≤90 and a decrease from Baseline of ≥20	mmHg
Vital Signs	Hypotension	Blood pressure diastolic	<50 and a decrease from Baseline of ≥15	mmHg

This document cannot be used to support any marketing authorization applications or variations thereof.

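### From Visit 4 onward, change in during- and post-infusion vital signs, and the blood-pressure flags, refer only to Day 1; add change from the same visit's predose reading

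*Protocol*

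**What the plan says.** **Reference value.** Protocol 14.2 sets one Baseline for the whole study: "Baseline will be the last non-missing data collected prior to the first dose of IMP in Dosing" Period 1. SAP 3.3 agrees: "Baseline will be the last available predose value prior to the first infusion of study drug in Dosing Period 1". For vital signs, SAP Table 3-1 gives "Clinical chemistry, Hematology, Urinalysis, ECG and Vital signs: Predose Day 1 or if missing the Screening value". Neither document defines a Baseline for Dosing Period 2 or for an individual visit.

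**Readings.** The vital-signs footnote to Protocol Table 5.1 states: "On dosing days, vital signs will be measured prior to IMP administration, 15 minutes after the start of the infusion", then at the end of the infusion and 2 and 4 hours after it. Protocol 12.3.3 gives the same schedule, with one reading "during the infusion (at the halfway time point), at the end of infusion, 2 hours after end of" infusion, and at 4 hours. Every dosing visit thus has its own predose reading and four later ones.

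**Analysis.** Protocol 14.4.1 covers pulse rate, "systolic/diastolic BP, temperature, and respiratory rate). Measured values and changes from" Baseline, by treatment group; SAP 11.4.1 summarises the same two quantities by time point. SAP 11.4.1 also lists every measurement by subject, with flags from Table 14-7. The low systolic criterion there is "≤90 and a decrease from Baseline of ≥20" mmHg. The high systolic criterion is a value of at least 180 with a rise from Baseline of at least 15mmHg. Change from the same visit's predose reading is not planned anywhere.

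**The concern.** Four readings during and after each infusion, with one just before it, are a schedule built to show acute effects. After the first dosing visit, the planned change score answers a different question. It adds whatever happened to the subject's blood pressure over the preceding weeks to whatever the infusion did. A subject whose pressure has drifted up since Day 1 can have a large fall during an infusion that looks modest. A subject whose pressure has drifted down can appear to react when little happened that day.

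This matters most in Dosing Period 2. Everyone receives active drug there, so no concurrent placebo group shows how much of a change is ordinary variation. Visit 9 is also the first active infusion for subjects who began on placebo.

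**Working it through.** **Step 1: what the planned change contains.** For a reading taken during or after an infusion,

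post - Day 1 = (post - same-visit predose) + (same-visit predose - Day 1).

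The first term is the acute change and the second is drift. Visits 4, 6, 9, 11 and 13 fall on Days 8, 15, 29, 36 and 43, so drift covers 7, 14, 28, 35 and 42 days, or 1 to 6 weeks. At Visit 2 the Day 1 predose reading is the same-visit predose reading, so drift is zero.

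**Step 2: effect on the flags.** The Table 14-7 systolic criteria applied with each reference (constructed values, mmHg):

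| Day 1 | Same-visit predose | Post | Change from Day 1 | Flag as planned | Same-visit change | Flag on same-visit change |
|---|---|---|---|---|---|---|
| 105 | 130 | 88 | -17 | no | -42 | yes |
| 130 | 108 | 90 | -40 | yes | -18 | no |
| 168 | 150 | 181 | +13 | no | +31 | yes |
| 150 | 182 | 184 | +34 | yes | +2 | no |

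The two references disagree in both directions, for falls and for rises.

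**Step 3: what the planned tables still give.** When the same subjects contribute, mean(post) - mean(predose) = mean(post - predose). Measured values are summarised by time point, so the group mean same-visit shift follows by subtraction. Its spread does not. Var(post - predose) = Var(post) + Var(predose) - 2 Cov(post, predose), and no planned summary gives that covariance. The median, minimum and maximum of same-visit change cannot be derived from the summaries either.

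**Step 4: possible size.** The documents give no SD or correlation for blood pressure, so these inputs are assumptions: mean systolic 125, SD 15mmHg, between-visit correlation r from 0.5 to 0.9, and SD w of same-visit change 6 or 10mmHg.

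- SD of change from Day 1 = sqrt(2 × 15² × (1 - r) + w²). The lowest value is sqrt(45 + 36) = 9.0 (r = 0.9, w = 6). The highest is sqrt(225 + 100) = 18.0 (r = 0.5, w = 10). The SD of same-visit change is 6 to 10.
- With no infusion effect, 1.3% to 13.3% of subjects show a fall of at least 20mmHg from Day 1. From same-visit predose the share is below 0.1% to 2.3%.
- With a true effect of -20mmHg (simulation, 400,000 draws per setting), the planned low systolic flag misses about 9% to 16% of those that a same-visit reference would raise. About 9% to 26% of the flags it does raise are not same-visit falls of at least 20mmHg.

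A simpler form with equal SDs gives a variance ratio of (1 - r between days)/(1 - r within day). With assumed correlations of 0.5 to 0.6 between days and 0.7 to 0.85 within a day, it runs from 0.4/0.3 = 1.3 to 0.5/0.15 = 3.3.

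**The case against.** The strongest reply is that little is lost. Every reading is listed by subject, so the 130 and the 88 of the first example both appear. The 88 also enters the measured-value summary for its time point. The flags sit in a listing and feed no planned count or test; vital signs are analysed descriptively throughout. Infusion reactions have their own route: at least 4 hours of monitoring after each infusion, adverse event recording, and a flag for infusion reactions in the adverse event listing (SAP 11.2). Nor is Dosing Period 2 without any comparison. Placebo-first subjects have their own placebo infusions at Visits 2, 4 and 6 on the same reading schedule, and the period randomises between two doses. The safety variables reviewed by the DMC are in a charter that is not part of these documents.

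All of this stands, and it limits the point to individual change scores, their distribution and the flags. It does not remove it. Adverse event capture depends on someone recognising a reaction, and the vital-sign analysis could check that objectively from data already collected.

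The reply is also right that Day 1 should stay. Protocol 4.2.1 and SAP 2.2.2.1 define the safety variable as change from Baseline at each scheduled assessment, and a pre-treatment reference suits criteria labelled treatment-emergent. It catches cumulative falls too: with 130 on Day 1, 107 predose and 88 postdose, the change is -42 from Baseline (flagged) but only -19 within the visit (not flagged).

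**Conclusion.** The point holds in a limited form. At Visits 4, 6, 9, 11 and 13 the planned change scores and blood-pressure flags for during- and post-infusion readings cannot separate an acute effect from 1 to 6 weeks of drift. The planned tables contain neither the distribution of same-visit change nor a flag on it. The disagreement between references follows from the definitions alone. The percentages in the working rest on assumed SDs and correlations and show only a plausible order of size.

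Two stronger readings should be resisted. A reader might infer that the plan hides or creates an infusion effect in the group results. It does not: the mean shift can be recovered, and the placebo-controlled first-dose comparison at Visit 2 is untouched. A reader might also infer that the analysis fails to reproduce the blood-pressure bands in Protocol Table 18.1. That table gives suggested management guidance with example signs and states no reference value for its changes, so it sets no standard for this analysis.

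This is a low-cost improvement to descriptive safety reporting. No primary or secondary efficacy result depends on it.

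**What to change.** In SAP 11.4.1, and in matching words in Protocol 14.4.1, **add** change from the same visit's predose value for the mid-infusion, end-of-infusion, 2-hour and 4-hour readings at each dosing visit. Summarise it by visit, time point, period and treatment group with n, mean, SD, median, minimum and maximum. Add a second listing flag that applies the Table 14-7 blood-pressure change limits to this variable, labelled so that it cannot be confused with the existing flag. Keep change from Day 1, and its flags, for all readings.

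Optionally, derive the same change for the 4-hour postdose cytokines at Visits 6, 9 and 13. Protocol Table 5.1 already schedules a predose sample at those visits, and SAP 10.5 summarises change only from the Day 1 value.

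The cost is one derived variable, some extra table and listing columns, and a few sentences of text. No new reading, visit or clinical rule is needed.
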